Participants will be instructed that the device is intended to provide effective relief of dyspnea. It will be further communicated to them that the device may or may not help them recover from shortness of breath.

The VitaBreath device is intended to relieve exertion-related shortness of breath in COPD patients. For the majority of patients, this would occur as a result of activities of daily living, such as retrieving the

Pilot Study to Assess the Effect of Providing Intermittent Positive Airway Pressure in COPD Patients in Order to Relieve Their Exertion Related Shortness of Breath

HRC-17007-VBIDEPILOT-PN

mail or climbing stairs. Although patients may use the device when participating in an exercise program that is not the primary intended use of the device.

Pursed Lip Breathing (Control condition)

Pursed lip breathing (PLB) is the standard of care and will be used as the control condition comparator.

STUDY DESIGN

This will be laboratory-based study with a 2-arm, randomized, controlled, crossover design where the participants will be tested with the investigational device VitaBreath and control condition (PLB) in a random order.

STUDY AIM

The aim of this study is to evaluate that intermittent positive airway pressure therapy given to COPD patients with the VitaBreath device will relieve their exertional dyspnea allowing them to walk further in a modified 6MWT.

STUDY OBJECTIVES

The primary objective will be to compare the distance walked in 6 minutes by COPD participants using Pursed Lip Breathing (PLB) versus an intermittent positive airway pressure handheld device, VitaBreath.

Primary Efficacy Endpoint: Distance walked as measured by modified 6MWT evaluated during the Study Intervention Visit

Primary Hypothesis

Participants will walk further during the modified 6-Minute Walk Test when using VitaBreath compared to pursed-lip breathing at the Study Intervention Visit.

SUBJECT SELECTION / ENROLLMENT

Participants will be identified by investigators at each site. Following IRB approval and after obtaining written informed consent, participants found to possibly meet criteria for participation will be screened to determine their eligibility. The inclusion and exclusion criteria of this study are listed below.

Pilot Study to Assess the Effect of Providing Intermittent Positive Airway Pressure in COPD Patients in
Order to Relieve Their Exertion Related Shortness of Breath
HRC-17007-VBIDEPILOT-PN

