The participant's medical history will include an assessment of their medication use, smoking history, and how often they rely on their rescue medication (at rest and with exertion). Any participation in a Rehabilitation Program will be captured as well.

Participants will be allowed to begin exercise assessments 15 minutes after their bronchodilator administration. Concomitant medication and any adverse events will be recorded. The Participants oxygen level will be monitored during the standard 6MWT by continuous finger pulse oximetry. If the participant is not currently prescribed and using supplemental oxygen and their oxygen level is

Pilot Study to Assess the Effect of Providing Intermittent Positive Airway Pressure in COPD Patients in Order to Relieve Their Exertion Related Shortness of Breath

HRC-17007-VBIDEPILOT-PN

consistently \leq 88% during the test, the test will be stopped and the participant will be excluded. If the participant is currently prescribed and using supplemental oxygen during the test and their oxygen level consistently falls \leq 88%, supplemental oxygen will be titrated during the test by trained study staff until their oxygen level persistently is at 90% or higher during the test. Oxygen equipment will be available at the sites.

We will follow the American Thoracic Society Statement Guidelines for the Six-Minute Walk Test which include the following criteria for immediately stopping a 6MWT: Intolerable dyspnea, leg cramps, staggering, diaphoresis, and pale or ashen appearance.

Device Training

Participants will be asked to train on the VitaBreath device to practice breathing with it. The purpose of this training period is to get the participant acclimated to the device prior to using it during the modified 6MWTs at the Study Intervention Visit. If the participants have trouble coordinating with the device or cannot tolerate the mouthpiece resulting in leaks from the nasal cavity, they will be excluded from the study.

All participants will also be asked to practice pursed lip breathing with proper instruction and training by site staff.

Randomization

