A medically trained clinician will be present during the test in case of adverse events.

Participants will be asked to perform two 6MWT assessments on the Study Intervention Visit. Borg assessments will be made prior to the start of each test.

For one of the tests, participants will be given the VitaBreath device and the other test will be with control condition, where the patients will be instructed to use pursed lip breathing. The order of these two tests will be randomized.

Test Procedure

In order to standardize the participant use of the devices, at the 3 minute mark the test will be stopped for 30 seconds. During this 30 second pause, study participants will be instructed to use the study device in order to help them recover from being short of breath. For the test where participants are randomized to not use a device, they will be instructed to use the pursed lip breathing technique to help them recover during the 30 second duration. After the 30 second pause, the participants BORG assessment will be made and then they will be instructed to complete the remaining 3 minutes of the walk test. At the end of the test, participants will be asked to sit down and their Borg assessment will be made every 30 seconds until they reach their baseline Borg.

Participants will be required to rest at least 30 minutes between tests.

Statistical and Analytical Plan

Descriptive Data

Descriptive data tables will be provided for all variables of interest. Continuous data will be presented by mean, standard deviation, median, minimum and maximum observation. Data will be presented in the untransformed and transformed format (if applicable) for each continuous variable. Categorical data will be presented as frequencies and percentages.

Pilot Study to Assess the Effect of Providing Intermittent Positive Airway Pressure in COPD Patients in
Order to Relieve Their Exertion Related Shortness of Breath
HRC-17007-VBIDEPILLOT-PN

Analysis Populations

The endpoint will only be analyzed among completed cases in this pilot study.

Primary Effectiveness Analysis

The data from this trial will be evaluated to determine whether they meet the assumptions of parametric methods. The distance walked during the modified 6MWT will be compared between VitaBreath and pursed-lip breathing, using either a paired t-test or the nonparametric Wilcoxon Signed Ranks test, depending on the distribution of the data. The significance level will be a two-sided alpha of 0.05.

Safety Analysis

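### Efficacy-intent wording is prescribed for the device only, with no common neutral statement for both conditions, in an unblinded comparison with an effort-dependent endpoint

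*Combined protocol and SAP*

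**What the plan says.** Under Study Interventions, VitaBreath (Investigational), the protocol prescribes what participants hear about the device: "Participants will be instructed that the device is intended to provide effective relief of dyspnea". The sentence after it reads: "It will be further communicated to them that the device may or may not help them recover from shortness of breath".

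The companion entry, Pursed Lip Breathing (Control condition), describes the comparator but prescribes no message to participants about what it is meant to achieve: "Pursed lip breathing (PLB) is the standard of care and will be used as the control condition comparator".

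Elsewhere the two conditions are treated more evenly. Device Training says: "All participants will also be asked to practice pursed lip breathing with proper instruction and training by site staff". In Test Procedure, participants in the device walk are "instructed to use the study device in order to help them recover from being short of breath". In the other walk, "they will be instructed to use the pursed lip breathing technique to help them recover during the 30 second duration".

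Study Design states: "This will be laboratory-based study with a 2-arm, randomized, controlled, crossover design". Neither that section nor any other describes a sham device, blinding of participants or a masked assessor. The primary endpoint is distance walked in the modified six-minute walk test.

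**The concern.** Participants know whether they are holding a device or breathing through pursed lips, and how far they walk depends partly on how hard they try. If they have been told that one of the two methods is meant to be effective, and have been told nothing equivalent about the other when it is introduced, they may try harder in the device walk.

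That shift belongs to the condition, not to the period. Randomizing the order balances learning and fatigue across the two walks, and using each participant as their own control removes differences between people. Neither touches an effect that occurs whenever the device is used. It passes in full into the paired difference that the primary test evaluates.

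Two things are at stake. The pilot comparison would mix the device effect with a suggestion effect to which the protocol itself contributes. And because the Sample Size section gives the pilot the job of supplying a power analysis for the pivotal trial, the mixed estimate would be carried forward.

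**Working it through.** **Is the messaging symmetric?** Taking each point at which the protocol says what participants are told or trained to do:

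| Point of contact | Device | PLB |
|---|---|---|
| Introduction (Study Interventions) | Efficacy-intent statement, then a hedge | No message prescribed |
| Training at screening (Device Training) | Practice with the device | Practice with instruction by site staff |
| Before the walks (Study Intervention Visit) | Renewed practice, up to 5–10 minutes | Coordinator's reminder to practise |
| Three-minute pause (Test Procedure) | Use it to help recovery | Use it to help recovery |

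The pause wording is balanced. The asymmetry lies in the introductory message, with a lesser difference in practice before the walks. No statement common to both conditions appears anywhere.

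**How large could the effect be?** The plan states no effect size, SD or power, so there is no figure to reproduce. What follows is an illustration with an assumed shift.

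Inputs from the documents: n = 20 (Sample Size); paired t-test or Wilcoxon signed ranks test at two-sided alpha 0.05 (Primary Effectiveness Analysis). The paired t-test is used here, and all 20 are taken to complete.

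Assumed: no true device effect, and a total expectancy shift of d SDs of the paired difference.

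Formula: with 19 degrees of freedom and critical value 2.093, the test statistic follows a noncentral t distribution with noncentrality d × √20 = d × 4.472. The rejection rate is P(T > 2.093) + P(T < −2.093).

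| d | Noncentrality | Rejects in favour of device | Rejects in favour of PLB | Total |
|---|---|---|---|---|
| 0 | 0 | 2.5% | 2.5% | 5.0% |
| 0.1 | 0.447 | 6.24% | 0.85% | 7.1% |
| 0.2 | 0.894 | 13.35% | 0.25% | 13.6% |
| 0.3 | 1.342 | 24.65% | 0.06% | 24.7% |

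In metres, for an assumed SD of the paired difference between 20 and 50 m, shifts of 0.1 to 0.3 SD run from 0.1 × 20 = 2 m to 0.3 × 50 = 15 m.

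**What carries over to the pivotal trial?** Assume a true effect of 0.3 SD, a paired two-condition pivotal trial sized for 80% power, and pivotal wording that removes the shift entirely. The correct size is then 90.

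- Pilot shift of 0.1 SD: planning effect 0.3 + 0.1 = 0.4, giving n = 52. Actual power at 0.3 SD is 56.5%.
- Pilot shift of 0.2 SD: planning effect 0.3 + 0.2 = 0.5, giving n = 34. Actual power at 0.3 SD is 39.7%.

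If the pivotal trial keeps the same wording, the same shift recurs there and the sample size is not wrong for this reason. The estimate would still not be the device effect alone.

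**The case against.** The strongest reply is that the message is mixed. The wording speaks of intent, the hedge follows at once, and Potential Benefits says that participation brings no direct benefit to the subject. PLB is not neglected either: it is taught, participants are reminded of it, it is their standard of care by inclusion criterion, and it is presented at the pause as an aid to recovery. A reader might infer from the introductory sentence that nothing comparable is ever said for PLB. Test Procedure shows otherwise. This part of the reply stands, and it narrows the point to the introductory message and the missing common statement. It does not remove the point: the hedge also concerns the device alone, and balanced wording at the pause does not withdraw an earlier device-only statement of effectiveness.

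Second, the rejection rates above apply to any bias of that size in any paired test with n = 20. Nothing in the documents ties this sentence to a given shift. A new device compared with a familiar technique would raise some expectancy under any script, so the sentence's own contribution could be close to zero. This stands in full, and the figures are illustrative only.

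Third, a reader might point to the primary hypothesis, "Participants will walk further during the modified 6-Minute Walk Test when using VitaBreath compared to pursed-lip breathing", as further suggestion to participants. It is the sponsor's hypothesis, and no section says that participants are told it. Nor can anything be said about the consent form, whose pages are not in the copy reviewed.

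**Conclusion.** The point holds in a limited form. Efficacy-intent wording is prescribed for the device only, is tempered but not withdrawn, and is not matched by a neutral statement covering both conditions. That the comparison is open-label is inferred from the absence of any described blinding or sham and from the nature of the two methods. On that basis, any expectancy created enters the primary paired difference, and the design does not remove it.

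Its size is unknown. The 7%, 14% and 25% rejection rates belong to assumed total shifts of 0.1, 0.2 and 0.3 SD with 20 completers and no true effect. A reader might take them as the false-positive rate caused by this sentence; the documents do not support that.

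A reader might also conclude that the pivotal trial will be underpowered. That follows only if the pivotal wording differs from the pilot's so that the shift shrinks or disappears. No figure stated in the plan changes. This is a modest weakness that is cheap to correct.

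**What to change.** Delete the efficacy-intent sentence and replace both introductory device sentences with one equipoise statement, used for both conditions at training and before each walk. For example: *In each walk you will use one of two methods during the pause. Either one might or might not help you recover, and we do not know whether one works better than the other.* This expresses uncertainty about the comparison without singling out PLB, the standard of care, for doubt. Keep the parallel pause instructions in Test Procedure. Check that the consent wording is consistent with the new statement. Use the same statement in the pivotal trial, so that the pilot estimate and the pivotal result are obtained under the same messaging.

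The cost is a wording amendment, IRB notification and brief site instruction, with no added visits, measurements or participants. The change does not blind the comparison. It removes only the part of the expectancy that the protocol's own wording may add.

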Participants with a diagnosis of COPD who experience shortness of breath may be eligible for participation in this study

Sample Size

This will be a 20 patient pilot study to provide a power analysis for the Pivotal IDE protocol. The previous engineering clinical study included three treatment conditions, whereas the planned pivotal design will only have two conditions, VitaBreath and pursed-lip breathing. This pilot study will test this new trial design.

Inclusion / Exclusion Criteria:

Inclusion Criteria	Exclusion Criteria

All participants:
 
• Age ≥ 40• Ability to provide consent• COPD diagnosis• FEV₁ <55 and ≥ 25 percent of predicted value• Perceived Shortness of Breath via the Modified Medical Research Counsel Dyspnea questionnaire (rating of 2 or greater) (Appendix B)• Able to follow directions• Able to tolerate mild physical activity• Pursed Lip Breathing as standard of care• No evidence of bullous lung disease (with any bullae greater than 3cm in diameter) as confirmed by a CT scan within the past one year.	
All participants:
 
• Subjects who are acutely ill, medically complicated or who are medically unstable as determined by the investigator.• Suffering from COPD exacerbation at time of enrollment or 60 days prior• Subjects who are not currently prescribed oxygen and manifest oxygen desaturation below 88% on the screening 6MWT• Subjects with heart disease or neuromuscular disease.• Subjects who are not prescribed short-acting bronchodilator medication• Patients who have experienced recent barotrauma or pneumothorax• Unstable angina or Myocardial Infarction during past month• Uncontrolled Hypertension (systolic blood pressure of >180mmHg and a diastolic >100mmHg)• Heart Rate >120 at rest• Subjects who have trouble coordinating their breathing with the device during the device training, or cannot tolerate the device mouthpiece resulting in leaks from the nasal cavity• Women of child-bearing potential (WOCP) who are pregnant, breast-feeding, or planning pregnancy during the course of the study. (WOCP must have a negative pregnancy test at every visit)

Pilot Study to Assess the Effect of Providing Intermittent Positive Airway Pressure in COPD Patients in
Order to Relieve Their Exertion Related Shortness of Breath
HRC-17007-VBIDEPILLOT-PN

Pregnancy Screening

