All women of childbearing potential, (defined as any woman, unless surgically sterile or postmenopausal for at least 1 year) must be instructed to contact the Investigator immediately if they suspect they might be pregnant while participating in this study. If a participant becomes pregnant, she will be discontinued from the study. Pregnancy urine tests of WOCP will be completed at each visit prior to CT scan or usage of the VitaBreath study device.

STUDY PROCEDURES

The study will be explained to the potential participant and sufficient time provided to the subject to ask questions regarding the study. Study related procedures will commence only after the informed consent is signed by the subject. This is a multi (2 or 3) visit study as part of which, participants will be asked to complete in-lab six minute walk tests.

Screening Visit/s 1 and 2 - Screening and Randomization

Recruited participants will be asked to report to the clinical site where consenting and screening related procedures will take place. After consenting, subject eligibility will be evaluated and the following will be collected, demographics, anthropometric measurements, concomitant medications, vital signs and medical history review at Screening Visit 1. WOCP will complete a pregnancy urine test at Screening Visit 1 prior to any CT scan.

The rest of the screening procedures may commence if a recent CT scan (in the past year) of the participant is available and confirms eligibility. If the study participant has not had a CT scan within the past year, they will be scheduled for one by study staff. The participants will be asked to return for Screening Visit 2 once the CT scan review confirms their eligibility.

If a Screening Visit 2 is required, WOCP will complete a pregnancy urine test prior to any usage of the VitaBreath study device at Screening Visit 2.

Upon confirmation of their CT scan review at either Screening Visit 1 or if needed, Screening Visit 2, participants will undergo the remaining screening procedures to assess study eligibility: spirometry, 6 minute walk test (Standard 6MWT)^{29,32}, device training/acclimation, and a dyspnea rating assessment (Modified Medical Research Counsel - Appendix B)³⁴.

Participants will be asked to take their short-acting bronchodilator medication 15 minutes prior to start of the 6MWT.

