The EPAP and IPAP pressures delivered by VitaBreath may predispose COPD participants with recent barotrauma, pneumothorax or a history of bullous lung disease (large bullae greater than 3cm in diameter) to greater risk. Therefore, these participants will be excluded from the study; per the inclusion criteria, patients must have no evidence of bullous lung disease (with any bullae greater than 3cm in diameter) as confirmed by a CT scan within the past one year. Additionally, severe COPD participants with <25% predicted FEV1 will also be excluded from the study.

Computed Tomography (CT) imaging uses ionizing radiation to generate images of the body but is conducted in the COPD population to provide detailed information regarding advancement and severity of the disease state. A CT scan has risks associated with ionizing radiation exposure that could include potential damage to DNA and a small increase in the possibility that a person will develop cancer later in life.³⁵ CT associated risks are increased for a fetus that is exposed to CT scans. Therefore pregnant women will be excluded from participating in the study. If a CT scan detects an incidental finding, the investigator may direct the participant to seek further health assessments through standard of care pathways.

Although the occurrence rates for barotrauma and pneumothorax are not well defined, should they occur at a rate greater than two occurrences, we will suspend the study for evaluation. If any other SAE occurs, we will critically evaluate it and decide continuance of the study accordingly. Death possibly related to the use of this product is unexpected, but we will stop the study if one Severe Unanticipated Device Related Adverse Event occurs.

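### Cheap improvement: for people with no CT in the past year, the study CT comes before spirometry and the mMRC, so some who fail those entry criteria may be scanned needlessly

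*Combined protocol and SAP*

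**What the plan says.** All references are to the combined protocol and SAP.

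- **Study Procedures, Screening Visit/s 1 and 2.** After consent, Screening Visit 1 covers demographics, body measurements, medications, vital signs and medical history. Women of child-bearing potential also have a urine pregnancy test before any CT. Other screening "procedures may commence if a recent CT scan (in the past year) of the participant is available and confirms eligibility". Failing that: "If the study participant has not had a CT scan within the past year, they will be scheduled for one by study staff". Then: "The participants will be asked to return for Screening Visit 2 once the CT scan review confirms their eligibility".
- **Same section, after CT review.** At that stage "participants will undergo the remaining screening procedures to assess study eligibility: spirometry, 6 minute walk test", followed in the list by "device training/acclimation, and a dyspnea rating assessment" on the mMRC scale.
- **Inclusion / Exclusion Criteria.** FEV1 must be "<55 and ≥ 25 percent of predicted value", and the mMRC rating must be 2 or greater. Bullae larger than 3 cm must be ruled out by a CT within the past year.
- **Risk and Discomforts.** The bulla criterion is explained by the inspiratory and expiratory pressures that the device delivers. On the scan itself: "A CT scan has risks associated with ionizing radiation exposure that could include potential damage to DNA and a small increase" in the chance of a later cancer.
- **Potential Benefits.** Participants are told to expect no direct benefit.

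**The concern.** The only screening step that uses ionizing radiation comes before two entry checks that use neither radiation nor the device. One of them is a five-grade questionnaire. A person without a recent CT who has, say, an mMRC of 1 or an FEV1 of 60% predicted could be scanned, return for a second visit, and only then be found ineligible. That scan would serve neither the person nor the study.

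The issue is participant burden and protection. It does not touch the primary endpoint, the paired comparison, the significance level or the sample size.

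**Working it through.** **1. The order of steps for a person with no CT in the past year**

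| Step | Content | Entry criterion tested |
|---|---|---|
| Screening Visit 1 | Demographics, body measurements, medications, vital signs, history, pregnancy test where relevant | Pregnancy, and whatever the history and vital signs show |
| Between visits | Study CT and its review | Bullae larger than 3 cm |
| Screening Visit 2 | Spirometry, standard 6MWT, device training, mMRC (order within this group not fixed) | FEV1, desaturation, coordination with the device, mMRC |

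The CT comes before the FEV1 and mMRC checks. I looked for any requirement of a measured or documented FEV1, or of an mMRC rating, before a study CT is ordered, and found none. The description of the medical history covers medication use, smoking, reliance on rescue medication and rehabilitation. It names neither measure.

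**2. Does the stated reason for the CT explain the order?**

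The reason given is the risk of positive pressure in people with large bullae. That supports having the CT before any use of the device, including training. It does not bear on spirometry or the mMRC. The plan already puts one simple check, the pregnancy test, ahead of the radiation.

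**3. Size**

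The plan gives no figure to reproduce. Two unknowns have to be assumed:

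- c: share of people who need a study CT, taken as the same in those who pass and those who fail
- f: share of those reaching the FEV1 and mMRC checks who fail one or both

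The planned 20 patients come from the Sample Size section. If 20 means people who pass screening, and other screen failures are ignored, the number reaching these checks is 20/(1 − f). Of these, 20f/(1 − f) fail, and a share c of the failures had a study CT:

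avoidable scans = 20 × c × f/(1 − f)

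| f | c = 50% | c = 100% |
|---|---|---|
| 0% | 0 | 0 |
| 10% | 20 × 0.5 × 0.1/0.9 = 1.1 | 20 × 0.1/0.9 = 2.2 |
| 30% | 20 × 0.5 × 0.3/0.7 = 4.3 | 20 × 0.3/0.7 = 8.6 |
| 50% | 20 × 0.5 × 0.5/0.5 = 10 | 20 × 0.5/0.5 = 20 |

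If 20 instead counts everyone who consents, the figure is at most 20 × c × f. For f = 10%, 30% and 50% that gives 1, 3 and 5 at c = 50%, and 2, 6 and 10 at c = 100%. If c = 0 (everyone has a recent CT on file), the count is zero on either reading.

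**The case against.** **Pre-selection.** Investigators identify participants, and only those thought possibly to qualify are screened. A COPD diagnosis is required, and eligibility is to be evaluated after consent with a history review before any CT. A site holding an FEV1 of 60% on file could stop there. This stands as a limit on how many people are affected. It does not remove the problem, because it is not a required FEV1 or mMRC check and a person without a recent FEV1 on file would pass through it.

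**Unknown size.** Nothing in the documents supports any particular f or c, and the upper rows of the table have no anchor. This stands in full. A reader might infer that many ineligible people will be scanned, but the documents do not support that. They support only that it can happen.

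**Timing of the mMRC.** A reader might infer from its last place in the list that the mMRC is rated straight after the walk test and device training, and is distorted by them. The documents do not support this. They list the procedures without fixing an order within the group, so a site may give the mMRC first. The scale in Appendix B also asks about everyday breathlessness, not breathlessness at that moment.

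**The screening 6MWT.** It does not use the device either, and it carries its own desaturation exclusion, so the same reasoning could reach it. That is fair. However, Risk and Discomforts attaches moderate and severe risks to exercise testing, so moving it would expose people later excluded for bullae to a test they now avoid. The change below leaves it where it is.

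**Existing safeguards.** CT risk is described in the protocol and pregnancy testing comes first. Both are true. Neither prevents a scan in someone who fails FEV1 or mMRC.

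**Conclusion.** The point holds as a cheap improvement. For participants with no CT in the past year, the protocol puts the study CT before spirometry and the mMRC, and requires no FEV1 or mMRC check beforehand. Some people who cannot qualify on those criteria may therefore be scanned, and the device-pressure rationale does not call for that order.

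Confidence in the sequence is high, since the text is explicit. Confidence in the size is low: avoidable scans run from zero upward. About 2 is an illustration that rests on all 20 enrolled needing a CT and 10% of those scanned failing FEV1 or mMRC. People with a usable CT from the past year are not affected.

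A reader might also infer that this weakens the trial's result. It does not: the order of screening tests changes who is scanned, not how the walking distances are compared.

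**What to change.** 1. In Study Procedures (Screening Visit/s 1 and 2), move the mMRC and spirometry to Screening Visit 1, and schedule a study CT only for participants who meet both the FEV1 and mMRC criteria.
2. Keep device training after CT review and the pregnancy test before any CT, as now.
3. Under Randomization, where the Study Intervention Visit is set within 5 ± 2 business days of screening, state which screening visit starts that window. With two possible visits the anchor is unclear, and the move makes it matter more.

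This is a protocol amendment that reorders existing procedures. It adds no procedure type, visit or staff. There are three downsides:

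- Screening Visit 1 becomes slightly longer.
- For those who need a CT, the qualifying FEV1 is older by the time taken to schedule and review the scan. The protocol sets no limit on that interval.
- Some people later excluded for bullae will have had spirometry that they would now avoid.

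In return, people who fail FEV1 or mMRC are spared both the scan and the return visit.
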